Cash: All payments will be conditioned on girls being enrolled in school. Enrollment will be verified during the second month of each term and payments made by the end of that month. Household heads that had an out of school girl ages 11-14 at the start of the intervention period will receive a one-time payment of 4500/ (~US\$ 41). In addition, household heads of all girls 11-14, regardless of baseline school status, will receive 1500/ (~\$13.50) each term thereafter (total of four payments). Cash transfers will be paid via Mpesa to the household head determined at the time of registration. If the household has more than one girl between the ages of 11-14, they will all be eligible for their own cash transfer.

In-Kind: Girls who are out of school at baseline will receive an in-kind incentive if they enroll in school during the first term of the 2022 school year. All girls still enrolled in school during the first term of the 2023 school year will receive another incentive. The exact incentive (e.g. a goat or a school supply kit) will be determined during the formative assessment to take place in Q1 2022. In addition, a community level enrollment target will be set at 10 percentage points above baseline enrollment. If the community meets the enrollment target at the end of the program, an in-kind project will be given that values approximately US\$5000 (e.g. building classrooms or latrines at the school) which will be implemented and monitored by the community conversation group members.

The arms are as follows:

6. Study Goals/Objectives

The overall objective of this study is to determine which modified version of the original AGI-K intervention model is optimized for scale up based on effect, feasibility and cost of delivery via government channels.

The study involves the evaluation of three different packages of interventions to enrol and retain out of school girls aged 11-14 and change social norms related to girls' education and child marriage, in Wajir. All three packages will include girls' empowerment groups and community engagement on gender attitudes, layered on top of existing school feeding programmes, plus:

- 1) In some communities, no additional incentive
- 2) In some communities, an in-kind incentive for the whole community for school enrolment and retention, as well as an in kind incentive for individual girls

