- 3) In some communities, a financial incentive conditional cash for households with girls aged 11-14, conditional on school enrolment and retention.

Based on this intervention and study design, the project will seek to answer the following questions:

- 1. What are the effects on school enrollment and retention of three different packages of interventions?
- 2. What are the effects of the interventions on gender norms attitudes at community level and timing of marriage?
- 3. What are the costs of the three different packages of interventions relative to: a) one another, b) effects of each package, c) AGI-K original model and d) benefits
- 4. Which package is most feasible for efficient delivery via existing government and community structures?

Key outcomes of interest include: % of out-of-school girls enrolled, % of enrolled girls retained each term, % of enrolled girls transitioning to the next school year, literacy and numeracy scores, individual and community level gender norms attitudes, # of weekly meals accessed at school, perceived role of school feeding in school enrolment, retention and learning, % unmarried girls who are married during the study period, cost-per girl and incremental cost per educational outcome, and cost per marriage averted/additional year unmarried (via modelling). Key monitoring indicators to tracked are: # of community conversation meetings held, # of safe spaces group meetings held, average group attendance %, # of individual in-kind incentives delivered, # of community incentives delivered, and # of cash transfers disbursed.

7. Overview Table:

		Data Ga	thering Activities	
	Formative Assessment	HH Listing	Baseline Survey	Endline Survey
Study population	Girls aged 11-14, mothers and fathers of girls aged 11-	Adult member in the household, all	Girls aged 11 to 14 and adult member in household	Girls aged 11-14 and adult member interviewed at baseline
	14, teachers, CHAs, CHVs and additional key stakeholders	households in study villages	in all study villages	
Sample size	8 girls, 8 parents, 2 male teachers, 2 female teachers, 8 community health workers and 8 additional key stakeholders	Approximately 15,000 households	1,500 girls & 1,500 parents/guardians in Wajir (50 girls per village)	1,500 girls & 1,500 parents/guardians in Wajir
Location of activity	Household	Household	Household	Household
Timing	February 2022	March/April 2022	March/April 2022	April/May 2023
Method	In-Depth Interviews	Short form	Interview	Interview

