8. Data Collection Activity 3: Baseline Survey

a. Sub	ject Population
	The study population is girls between the ages of 11 to 14 residing in the 30 selected study villages in Wajir. The participants for the baseline survey will be approximately 1,500 girls between aged 11 to 14 (~500 per arm). In addition, in each household, the parent/guardian who provides consent for the girl to participate in the survey will also participate in a short interview on the household characteristics (1,500 parents/guardians in Wajir).
	All girls between the ages of 11 and 14 during the time of the survey, residing in study villages will be listed from the household listing above and households will be randomly selected for the baseline interview. In households with more than one eligible girl, only one will be interviewed.
	All eligible girls who consent to the interview will be interviewed at baseline. Once the survey is complete, villages will be randomly assigned to study arms during a public lottery. Once randomization is completed, girls, households and community members will be invited to participate in the various components of the programmes, based on their assigned study arms. Mentors and other programme staff will visit the girl in her home and discuss the benefits of the programme with both the girl and her parent/guardian. They will then invite the girl to participate in the programme, obtain the necessary consents and follow-up with the girl to ensure that she has enrolled in programme activities.
b. Res	earch Protocol
	The baseline survey will be conducted between March and April 2022, before intervention activities take place. This period was chosen so that the intervention can start at the end of April which is the start of the 2022 school year (delayed because of COVID-19).
	Due to the sparse geography in Wajir, the research team will arrive in a village and use 1-2 days to complete the household listing. Immediately following they will spend the next 2-5 days completing the baseline survey.
	Trained interviewers will be grouped into teams of 5-8, each team with a supervisor to provide directly quality assurance at the time and location of interviewing. The data

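### Retention and transition are counted among enrolled girls, a group the incentives change after the lottery, so comparing arms on them is not a randomised comparison

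*Protocol*

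**What the plan says.** Section 6 (Study Goals/Objectives) asks as its first question: "What are the effects on school enrollment and retention of three different packages of interventions". The outcome list that follows opens with "Key outcomes of interest include: % of out-of-school girls enrolled" and continues with the percentage "of enrolled girls retained each term, % of enrolled girls transitioning to the next school year". It does not say at what date a girl must be enrolled to count in the last two.

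The same section describes the study as an "evaluation of three different packages of interventions to enrol and retain out of school girls aged 11-14".

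The Baseline Survey activity in section 8 gives the order of events: "Once the survey is complete, villages will be randomly assigned to study arms during a public lottery". What happens next differs by arm (section 5, Education Conditional Transfers):

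- Cash arm: "Household heads that had an out of school girl ages 11-14 at the start of the intervention period will receive a one-time payment", conditioned on enrolment. A further KES 1,500 per term is paid for every enrolled girl aged 11-14, whatever her baseline school status.
- In-kind arm: "Girls who are out of school at baseline will receive an in-kind incentive if they enroll in school during the first term" of 2022. Girls still enrolled in term 1 of 2023 receive a second incentive.
- Third arm: neither incentive.

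**The concern.** A randomised comparison needs a denominator that the treatment cannot alter. Here the treatment is meant to alter it: a successful incentive brings more previously out-of-school girls into the enrolled group, so that group is a different mix of girls in each arm. If these girls stay in school at a different rate from girls already enrolled, the arms differ on retention even when the incentive changes nobody's chance of staying. Because retention is counted term by term, the same applies to girls already in school whom the per-term payment keeps in the denominator for the next term.

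One outcome in the list, enrolment among out-of-school girls, has a denominator fixed before the lottery, but it measures entry and not staying. No retention or transition outcome is given on all baseline girls or by baseline school status.

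The study's purpose is to choose the version best suited to scale-up, and section 6 lists incremental cost per educational outcome among the key outcomes. A retention contrast that mixes effect with composition can enter that choice directly.

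**Working it through.** **Figures in the protocol.** Survey size: 30 villages × 50 girls = 1,500, or 500 per arm, as stated. The Background gives 75% of Wajir girls in school at baseline in the earlier trial and 95% with cash transfers. That matches uptake of 80% among out-of-school girls: 75% + 25% × 80% = 95%. The protocol gives no retention rates and no uptake without incentives, so those values below are assumptions.

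**Notation.** b = share in school at baseline; e = share of out-of-school girls who enrol; rB, rN = retention of baseline-enrolled girls and new enrollees.

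- Enrolled share: E = b + (1−b)e
- Retained among enrolled girls: [b·rB + (1−b)e·rN] / E
- Enrolled and retained among all girls: b·rB + (1−b)e·rN

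**Step 1. No effect of the incentive on retention.** Take b = 75%, rB = 97% and rN = 80% in both arms, with e = 20% (no incentive) against 80% (cash).

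- No incentive: (0.75×0.97 + 0.05×0.80)/0.80 = 0.7675/0.80 = 95.9%
- Cash: (0.75×0.97 + 0.20×0.80)/0.95 = 0.8875/0.95 = 93.4%
- Difference among enrolled girls: −2.5 points. Among all girls: 76.8% against 88.8%, +12 points.

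The −2.5 is pure composition. When retention is the same in both arms, the difference equals (rN − rB) × (difference in the new enrollees' share of the enrolled). That share is 0.05/0.80 = 6.25% against 0.20/0.95 = 21.05%, so −17 × 0.148 = −2.5. The sign depends only on whether new enrollees stay less or more often than the others; if they stay equally often, the difference is zero. Retention pairs (rB, rN) of 97/80, 95/70 and 97/90 crossed with uptake of 20% v 80% and 30% v 70% give −0.7 to −3.7 points.

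**Step 2. The incentive may also improve retention.** Take b = 75%, e = 30% v 80%, rB = 95% without incentive:

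| Retention assumed (no incentive v cash) | Enrolled girls | All girls |
|---|---|---|
| New enrollees 70% in both | 92.7 v 89.7 (−3.0) | 76.5 v 85.25 (+8.75) |
| New enrollees 80% in both | 93.6 v 91.8 (−1.8) | 77.25 v 87.25 (+10.0) |
| New enrollees 95% in both | 95.0 v 95.0 (0) | 78.4 v 90.2 (+11.9) |
| New enrollees 70% v 90% | 92.7 v 93.9 (+1.2) | 76.5 v 89.25 (+12.75) |
| Baseline-enrolled 95% v 99%, new 70% in both | 92.7 v 92.9 (+0.2) | 76.5 v 88.25 (+11.75) |
| Both gains together | 92.7 v 97.1 (+4.4) | 76.5 v 92.25 (+15.75) |

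In the fifth row a true 4-point gain among girls already in school shows as 0.2. With uptake of 20% v 50% and 40% v 80% also tried, the enrolled-girls difference runs from about −3 to +5 points, while the all-girls difference stays between about +5 and +16.

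**Step 3. Lower baseline enrolment.** The Geographical Setting says two-thirds of girls aged 6-17 have never been to school. With b = one third, rB = 95%, rN = 70% in both arms and e = 30% v 80%: 85.6% v 79.6% among enrolled girls (−6.0), and 45.7% v 69.0% among all girls (+23.3).

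**The case against.** **Enrolled may mean enrolled at baseline.** The first two outcomes could be a pair by baseline status: out-of-school girls become enrolled, girls already enrolled are retained. That would remove the bias. The text does not say so, and the stated aim of enrolling and retaining out-of-school girls, together with a count each term, points the other way. On the baseline reading, retention of the very girls the study targets would have no outcome. Either way the date has to be stated.

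**This is detail for an analysis plan.** The list consists of short labels, and a protocol may leave exact definitions for later. But the denominator is written into the outcome, so this is more than a detail left open.

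**The two contrasts measure different things.** This stands. In step 1 the +12 points are entirely the assumed uptake gap: (0.20 − 0.05) × 0.80 = 0.12. It is not a retention effect. The illustration shows only that the enrolled-girls figure moves when nothing about retention differs.

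**Fixed-denominator information is already planned.** School registers track enrolment among children aged 5-14 from the household listing, and the endline survey seeks every baseline girl. A gap in enrolment would be visible, and packages are judged on feasibility and cost too. This limits the harm, but it does not redefine retention or transition.

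**A reader might infer that the incentive arms will look worse.** The documents do not support that. They give no retention rate by baseline school status, and both incentives also reward staying enrolled, so the contrast can come out on either side.

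**Conclusion.** The point holds as a defect of outcome definition. On the natural reading, two key outcomes serving the first research question compare arms within a group formed after randomisation and changed by the treatment, so they do not estimate a randomised effect on retention or transition.

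The size and direction of the bias are unknown. An arm that enrols more out-of-school girls can look worse at retention when retention is the same in every arm: by 2.5 points in the main illustration, and by 0.7 to 3.7 across the assumed rates tried there. This requires new enrollees to stay less often than girls already in school, which is plausible but undocumented. Once the incentives are also allowed to improve retention, the contrast ranges from about −3 to +5 points at 75% baseline enrolment. It does not follow that the outcomes are biased against the incentive arms, or that the ranking of packages will reverse. All retention rates and the no-incentive uptake are assumptions; only the 75% and the 95% come from the protocol.

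**What to change.** Define retention and transition in section 6 on groups set before the lottery:

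1. Among girls in school at baseline, and separately among girls out of school at baseline: the percentage enrolled at each 2022 term, from the registers, for all listed girls aged 11-14.
2. In the same two groups: the percentage enrolled, and the percentage moved to the next school year, in 2023, from the endline survey of about 1,500 girls.
3. Among all baseline girls: the percentage enrolled at the same times.

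Girls who never enrol stay in the denominator and count as not enrolled and not moved up. Keep the percentages of enrolled girls as descriptive monitoring, without comparing arms on them.

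The cost is small. For surveyed girls the data are already planned. For all listed girls, confirm that the listing form records school status in every village before the lottery; the incentives need that status in two arms, and the May 2022 register check comes too late to supply it. The 2023 figures are limited to surveyed girls because the School Enrollment Data activity plans register checks only for the 2022 terms. Extending them to all listed girls in every arm would need a further register visit.

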	As part of the Population Council's monitoring program, the subject will be asked to acknowledge the possibility that an interview may be requested by a representative of the Population Council to determine if informed consent occurred. If an interview is requested, the subject will have the option of accepting or declining the interview.

f.

	If the girl is under 18 years of age, written informed consent from a parent or guardian will be obtained prior to the interview. Written assent from the girls will also be obtained separately for the interview. For married girls, who are considered to be emancipated minors, informed consent for the interview will be obtained only from the girl.
	Written consent from parents/guardians and participants will be obtained prior to conducting in-depth interviews. Consent forms will inform the respondents the purpose of the study, that the interviews will be recorded, and that the information will be transcribed, stored and analyzed without any identifying information.
8. Dat	a Gathering Activity 2: Household Listing
a. Sub	ject Population
	In the 30 villages selected for the study the research team will screen and list all members of households that have an adolescent girl between the ages of 10 and 15 (approximately 15,000 to 20,000 households). The respondents will be adults (age 18+) residing in each household, or an emancipated minor if they are the head of the household. The household listing will allow us to identify eligible adolescent girls, between the ages of 11 and 14 in each household. The listing form will also collect basic information on household characteristics that will be used to determine eligibility for the intervention and support program recruitment.
b. Res	earch Protocol
	The household listing will be conducted between March and April 2022. Trained research assistants will visit every household, identify an adult who can answer questions about members of the household, and interview them using a short form (see Annex 2) to collect the required information. They will begin by asking several screener questions. If there is at least one girl between the ages of 10 and 15 residing in the household, they will complete the household roster and the brief background questionnaire on household characteristics. Interviewers will make up to three visits at different time schedules to each household if there is no one present.
c. Risk	as and Benefits to Subjects

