	Participants will have the opportunity to experience mainly indirect benefits from the study, in the sense that the information they are providing will directly inform the development of scalable interventions to improve the lives of adolescent girls. Participants in Wajir and in intervention sites in Nairobi will directly benefit through the interventions that will be implemented in their communities or that they will participate directly based on their assigned study arm.
d. Ste	ps to Minimize Risks
	To minimize the risk of loss of privacy, data will be collected using biometrics and mobile phones or electronic data capture and will be stored on password-protected computers at the Population Council office. In addition, no identifying information will be included in the data provided by the financial institution.
e. Con	e fidentiality
	Steps to ensure confidentiality of monitoring data are the same as those described for the Baseline Survey, above.
f. Con	npensation
	The participants will not be paid for the collection of monitoring data.
g. Info	ormed Consent Process
	After the completion of the baseline survey and randomization to study arms, girls and their parents/guardians will be invited to participate in the program and informed about the intervention activities and the types of monitoring data that will be collected as part of the intervention. Both parents/guardians and girls will be asked to sign consent/assent forms for program participation, that includes collection of monitoring data as described above. A separate form will be developed for each arm to describe the interventions/monitoring activities unique to each arm (i.e. education attendance, group attendance and account transactions).
8. Dat	a Collection Activity 7: School Enrollment Data
a. Sub	ject Population
	The study population is all girls and boys 5-14 years old residing in the 30 study villages. This list will be derived from the household listing (see above). We are including

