the household. b. Research Protocol ☐ School enrolment data will be verified three times throughout the life of the study – once per school term for the 2022 school year. ☐ School enrolment data will be used for two key purposes: 1) to determine eligibility for cash transfers and in-kind incentives and 2) track overall levels of school enrolment among 5-14 year olds in the study villages. ☐ Data collectors will visit the school administrator once per term with the enrolment register and confirm which students are enrolled. c. Risks and Benefits to Subjects RISKS ☐ The collection of monitoring data will not increase risk for girls or boys because their anonymity will be maintained using a unique ID, and no identifying information will be included in data provided by the financial institution. ☐ There is a minor risk of loss of privacy due to the collection of contact information for tracking purposes. **BENEFITS** ☐ There is no direct benefit to the school administrators. d. Steps to Minimize Risks ☐ To minimize the risk of loss of privacy, data will be collected using electronic data capture and will be stored on password-protected computers at the Population Council office. e. Confidentiality ☐ Steps to ensure confidentiality of monitoring data are the same as those described for the monitoring data above. f. Compensation ☐ The participants will not be paid for the collection of monitoring data. g. Informed Consent Process ☐ After the completion of the baseline survey and randomization to study arms, girls and

their parents/guardians will be invited to participate in the program and informed about

younger school aged children to be able to assess effects on enrolment of all children in

the intervention activities and the types of monitoring data that will be collected as part of the intervention. Both parents/guardians and girls will be asked to sign consent/assent forms for program participation, that includes collection of monitoring data as described above. A separate form will be developed for each arm to describe the interventions/monitoring activities unique to each arm (i.e. education attendance, group attendance and account transactions).

9. Data Management

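### Activity 7 tracks village-wide enrolment at ages 5-14 from a household listing that rosters only households with a girl aged 10-15, so the village-wide denominator cannot be derived as described

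*Protocol*

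**What the plan says.** Three parts of the Protocol bear on this.

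- **Section 8, Activity 7 (School Enrollment Data).** Under Subject Population: "The study population is all girls and boys 5-14 years old residing in the 30 study villages". The next sentence takes the list of children from the household listing. Under Research Protocol, the second of two purposes is to "track overall levels of school enrolment among 5-14 year olds in the study villages". The reason given for including younger children is narrower: to see effects on the enrolment of every child in the household.
- **Section 8, Activity 2 (Household Listing).** Under Subject Population, the task is stated thus: "screen and list all members of households that have an adolescent girl between the ages of 10 and 15 (approximately 15,000 to 20,000 households"). Under Research Protocol, every household is visited and asked screener questions, and then: "If there is at least one girl between the ages of 10 and 15 residing in the household, they will complete the household roster".
- **Section 7, Overview Table.** The enrolment column repeats the population of all children aged 5-14 in the study villages. The listing column gives its population as all households in those villages and its size as "Approximately 15,000 households".

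**The concern.** The named source cannot produce the named population. A village-wide enrolment level needs every resident child aged 5-14 in the denominator, in school or not. The listing captures those children only in households that also contain a girl aged 10-15.

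The omission is systematic. The retained households are those with a girl in or near the target ages of 11-14. The enrolment of their children need not match that of children in other households, before or after the intervention. A county government weighing scale-up could read a figure labelled as the level for the villages as covering children whom the study never listed.

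**Working it through.** The protocol states no figure to reproduce: it gives no count of children aged 5-14 and no roster coverage. The check is to follow the listing rule for each kind of child.

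**1. Who is listed, among households that are reached and respond**

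| Resident child | Girl 10-15 in the household? | On the roster? |
|---|---|---|
| Girl 10-14 | Yes, herself | Yes |
| Boy 5-14 or girl 5-9 | Yes | Yes |
| Boy 5-14 or girl 5-9 | No | No |

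The third row belongs to the Activity 7 population but is absent from its source list.

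**2. Whether the school register fills the gap.** Under Activity 7, data collectors confirm each term which students are enrolled. That identifies children in school. It does not identify resident children who are out of school, so it supplies a numerator without the missing part of the denominator.

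**3. Whether the household counts show the coverage.** The overview table gives about 15,000 for all households, or 15,000 / 30 = 500 per village. The listing text places "approximately 15,000 to 20,000 households" directly after the households with a girl aged 10-15, or 500 to 20,000 / 30 = 667 per village. Read literally, the subset would be 15,000 / 15,000 = 100% to 20,000 / 15,000 = 133% of the whole. The figures therefore cannot be used to work out what share of households is rostered.

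**4. What the gap could do to a level (illustration only).** Let c be the share of children 5-14 living in rostered households, and let p_in and p_out be the enrolment rates in rostered and other households. The village rate is c × p_in + (1 − c) × p_out, while the listing yields p_in. The error is

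(1 − c) × (p_in − p_out).

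No input is in the protocol. Assumed values give, in percentage points:

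| c | gap of 5 | gap of 10 | gap of 20 |
|---|---|---|---|
| 0.4 | 3 | 6 | 12 |
| 0.6 | 2 | 4 | 8 |
| 0.8 | 1 | 2 | 4 |

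The range is 1 to 12 points. Its sign follows the sign of p_in − p_out, which is unknown. The table shows only that the gap is not negligible by construction.

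**The case against.** The strongest reply is that only children in the girls' own households were ever meant. The stated rationale is within-household, and the roster rule serves it well. This stands as a reason to prefer the narrower restatement. It does not remove the conflict, because the population, the second purpose and the overview table are all worded for the whole village.

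A second reply is that every household is visited. That is true of screening, but the roster condition still applies afterwards. The screener form (Annex 2) is not at hand and might count all children. The listing section describes no such step, so this is a possibility and not an answer.

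A third reply is that little depends on it. Much of this stands. The key outcomes in section 6 concern girls, gender norms, school meals and cost, and enrolment of all children aged 5-14 is not among them. The listing precedes randomization and follows one rule in every arm, so the rule does not by itself bias comparisons between arms among rostered children.

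Three stronger readings are tempting and are not supported:

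- **That no denominator exists.** A partial one does: children 5-14 living with a girl aged 10-15.
- **That a village-wide effect would be overstated in the incentive arms.** Suppose 40-70% of children are in rostered households, with an effect of 8 points there and 0-2 points elsewhere. The village effect is then 0.4 × 8 + 0.6 × 0 = 3.2 to 0.7 × 8 + 0.3 × 2 = 6.2 points, so 8 points would overstate it 8 / 6.2 = 1.3 to 8 / 3.2 = 2.5 times. All of these inputs are assumed, and the result comes from setting the outside effect near zero. With 8 points outside as well, the ratio is 1. All arms have community conversation groups and the in-kind arm has a community reward, so effects elsewhere are plausible. The stated purpose is also to track levels, not to estimate a village-wide effect.
- **That the household counts prove a confused roster definition.** The parenthesis follows wording that covers both screening and listing, so it may count households screened. It is ambiguous, and no more than that.

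**Conclusion.** The point holds as a contradiction within the protocol: the village-wide population and purpose in Activity 7 cannot be met from the listing in Activity 2. Followed as written, the reported level would come from a selected subset. This is a rule that does not work, and not detail left to an analysis plan. It should be corrected, but its reach is limited. Girls aged 10-14 are covered by the roster rule, and so the baseline sampling frame of girls 11-14 and their eligibility for individual incentives are intact.

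Neither the size nor the direction of the error can be determined from the protocol. The conclusion rests on the listing being carried out as section 8 describes it, with no further count of children on the unseen form.

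**What to change.** Choose one of two changes.

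1. **Narrow the claim.** Restate the Activity 7 population, its second purpose and the overview table entry as children aged 5-14 in households with a girl aged 10-15. This agrees with the household-level rationale already given. Do not report the result as a village-wide level. This costs wording only.
2. **Widen the listing.** If a village-wide level is wanted, have the screener record the age, sex and school status of children 5-14 in every household visited. The households are already on the route, but the added time is real. The protocol allows 1-2 days of listing per village. At about 500 households and, as an assumption, one team of 5-8 interviewers per village, the load is already between 500 / (8 × 2) = 31 and 500 / (5 × 1) = 100 households per interviewer per day.

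Under either option, state whether the 15,000 and the 15,000-20,000 figures count households screened or households rostered, and use one definition in both places.
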